	Episodic Memory – Picture Sequence Memory Test (Bauer et al., 2013; Dikmen et al., 2014)			
	GL al., 2014)			
	Language – Oral Reading Recognition Test			
	Language – Picture Vocabulary Test (Dunn & Dunn, 1981)			
	Processing Speed – Pattern Comparison Processing Speed Test (Carlozzi et al., 2014)			
	Working Memory – List Sorting Working Memory Test (Weintraub et al., 2013)			
	Dexterity – 9-hole Pegboard Dexterity Test (Wang, Bohannon, Kapellusch, Garg, & Gershon, 2015)			
	 Strength – Grip Strength Test (Hamilton, Balnave, & Adams, 1994)			
	odoligin - Olip odoligin rest (riaminton, Dalliave, & Adams, 1994)			

PROMIS measures self-report of emotional functioning (Cella et al., 2007)

Each test in this panel is age normed. Therefore even though subjects will be of different ages, the change in their performance as a percentage of the normed values will be relevant and comparable from subject-to-subject. There are also published test-retest standard deviations from which to ascertain how much of a change in score is needed for a change to be regarded as significant.

Secondary Outcome Measures:

Secondary outcome measures include: change in quantitative EEG (power asymmetry), SWS clinical neuroscore, and birthmark score.

Another secondary outcome measure will be an assessment of impact upon seizures. Parents/caregivers will report the following before starting study drug and at each visit:

- Number of seizures (specifically motor seizures) This is the most reliable and important seizure outcome.
- Seizure duration
- Seizure Type
- Number of episodes of status epilepticus, defined as generalized convulsive seizure lasting longer than 10 minutes
- Number of uses of rescue medication.
- Number of ER visits/ hospitalizations for seizures

Statistical Considerations (sample size and analysis plan):

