Results of the above tests will be compared to age normed values. In addition, the difference in results between final test results and initial test results will be obtained for the cognitive functioning score of each subject. Mean and standard deviation of this difference for all 10 subjects will be calculated. These results will be used to determine whether individuals and the group as a whole demonstrated age normed changes in their cognitive functioning over the course of the six month trial. Neuropsychological testing will occur at both sites, KKI and CCHMC, and the deidentified results will be sent to KKI for analysis. There is no control group in this study of subjects who are not receiving study drug. The published test-retest standard deviations will be used to determine whether changes in testing results exceed expected test-retest changes in results.

Expected seizure rate can vary greatly both between subjects and for an individual. Subjects must be on the same AEDs for the past three months to join the study. Subjects whose seizures increase to the point where it is necessary to add another seizure medication, start the ketogenic or Atkins diet, or go for surgery to control their seizures will be removed from the study.

Quantitative EEG: An EEG will be done prior to starting study drug and at the end of the study while still on study drug. An asymmetry in power (roughly an integration of amplitude and frequency) in the affected side of the brain compared to the unaffected (or less affected) side of the brain, will be quantified as previously described (Hatfield et al., 2007; Ewen et al., 2009) for the quantitative EEG analysis. EEGs will occur at both sites, KKI and CCHMC, and the de-identified EEGs will be sent to KKI for analysis. The reason for this analysis is as a non-invasive biomarker of brain function which could be useful to develop as a marker of drug response. Quantitative EEG power analysis reflects an integration of the EEG activity amplitude and frequency. Therefore asymmetry of power on qEEG for these subjects reflects the increased slowing and decreased amplitude frequently seen in these patients interictally as their neurologic involvement progresses. Even patients with bilateral brain involvement have more involvement on one side than on the other side. Power asymmetry on qEEG has been shown to correlate with brain perfusion, brain atrophy, and SWS neuroscore, therefore, it has the potential as a biomarker responsive to

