Strength - Grip Strength Test (Hamilton, Balnave, & Adams, 1994)

PROMIS measures self-report of emotional functioning (Cella et al., 2007)

Each test in this panel is age normed. Therefore, even though subjects will be of different ages, the change in their performance as a percentage of the normed values will be relevant and comparable from subject to subject. There are also published test-retest standard deviations from which to ascertain how much of a change in score is needed for a change to be regarded as significant.

 Neuro-QOL scale will be collected at each visit. The Neurologic Quality of Life (Neuro QoL) will be collected prior to starting study drug and at each study visit. Descriptive statistics for this measure will be reported in the form of median and range. Mann Whitney U Test will be used to assess whether a significant change in quality of life has occurred after treatment compared to prior to treatment. NeuroQoL will be collected at both sites, KKI and CCHMC, and the de-identified results will be sent to KKI for analysis.

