5.9 Quality Control: Study Related Procedures

- 1. Clinical coordinators at both sites will review the case report forms after completion by [name] or [name] to resolve any issues.
- 2. [name] and [name] will review the study progress regularly with monthly phone conferences. The two sites will have internal reviews performed regularly to ensure high quality of the study procedures and subsequent data.
- 3. The DMCC will perform an audit of the overall protocol including this pilot project.

6. Statistical Considerations

The proposed trial is a pilot drug trial. Based on the results, a sample size calculation will be done, using the cognitive outcome with the greatest response to the study drug, to plan a follow up randomized, placebo-controlled trial, should one be warranted. If no serious adverse events which are thought to probably or possibly be due to the study drug AND the cognitive data suggests a trend for possible benefit, then the results of this study will be used to plan a larger follow-up clinical trial.

Children and adults between 3 and 31 years of age with Sturge-Weber syndrome brain involvement and cognitive impairments will be eligible for this pilot study. A total of 10 patients will be enrolled at two centers including Cincinnati Children's Hospital Medical Center and the Kennedy Krieger Institute. This sample size was selected based on 1) availability of potential appropriate subjects at both centers and 2) upon the investigators experience with similar clinical trials.

Cognitive tests proposed have been previously validated in the literature and are normed to aged matched normal controls. These are published tests which are widely used. Therefore, responders in this trial will be subjects whose normed results improve on the task more than what is expected for the increase in age (6 months) +/- expected standard deviation.

Anticipated number of patients to be enrolled:

Table 4

	American Indian or Alaskan Native	Asian or Pacific Islander	Black, not of Hispanic Origin	Hispanic	White, not of Hispanic Origin	Other or Unknown	Total
Female	0	1	1	0	3		5
Male	1	0	0	1	3		5
Total	1	1	1	1	6		10

7. Data Management

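### Does the cognitive responder rule need a stated SD, multiplier and sign before it can be used?

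*Combined protocol and SAP*

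**What the plan says.** Section 6 (Statistical Considerations) notes that the cognitive tests are "normed to aged matched normal controls" and then defines response task by task: "responders in this trial will be subjects whose normed results improve on the task more than what is expected for the increase in age", with the age term and margin written as "6 months) +/- expected standard deviation". It gives no value, type, multiple or sign for that SD.

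Three other places bear on it:

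- The Synopsis (Primary Outcome Measures) and Section 5.3 (neuropsychological testing) say "Each test in this panel is age normed". Both add that published test-retest SDs exist from which to judge "how much of a change in score is needed for a change to be regarded as significant".
- The Synopsis (Statistical Considerations) says: "The published test-retest standard deviations will be used to determine whether changes in testing results exceed expected test-retest changes in results". It also plans the mean and SD of the final-minus-initial difference over all 10 subjects, and says the results will be used to judge change in individuals as well as in the group.
- The same Synopsis section states: "There is no control group in this study of subjects who are not receiving study drug".

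Section 6 makes planning of a larger trial depend on two things: no serious adverse event thought probably or possibly due to the drug, and that "the cognitive data suggests a trend for possible benefit". It does not mention a responder count there. The only significance level in the document, 0.05, is set for the biomarker correlations.

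**The concern.** A threshold of the form more than X plus or minus an SD is not a threshold until someone says which edge applies, which SD is meant and how many of them. Two analysts working from the Section 6 sentence could classify the same subject differently. Change in cognition is called the primary outcome measure, and this is the only place where a responder is defined. With no untreated arm, the trial cannot show its own chance rate, so the cut-off is the only benchmark for a count of responders. Two responders of 10 on a task could be presented as encouraging or as noise, depending on a choice made after the data are seen. The rule is also silent on practice gain, and its six-month age term could be read as a second age allowance on scores that are already age-normed.

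**Working it through.** **Inputs.** From the document: 10 subjects, one baseline test and one retest at six months, age-normed scores, no control group. The document states no SD value, multiplier or responder rate, so there is no figure of its own to reproduce. Assumed: retest change is normal with mean zero after norming, there is no drug or practice effect, and the SD is that of the test-retest difference.

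**Step 1: which readings survive.** Read literally, plus-or-minus would allow three cut-offs c, in SDs of change, with chance rate 1 − Φ(c):

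- c = −1: 84.1%
- c = 0: 50.0%
- c = +1: 15.9%

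The first would label as a responder someone who falls almost one SD below expectation. That contradicts both the requirement in Section 6 to improve by more than expected and the Synopsis requirement to exceed expected retest change. The second ignores the SD that Section 6 names. Read with the Synopsis, the margin is positive and is built on the test-retest SD.

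**Step 2: what the missing multiplier leaves open.** Over 10 subjects, P(2 or more) = 1 − (1−p)^10 − 10p(1−p)^9.

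| Multiplier | Chance rate p per task | Expected of 10 | P(2 or more of 10) |
|---|---|---|---|
| 1 | 15.9% | 1.6 | 48.7% |
| 1.645 | 5.0% | 0.5 | 8.6% |
| 1.96 | 2.5% | 0.25 | 2.5% |

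The spread in p is 15.9/2.5, about sixfold.

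**Step 3: sensitivity to the type of SD.**

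- If the SD were a standard error of measurement, one SD would be c = 1/√2 = 0.707, and the rate 24.0%.
- If it were a normative SD with retest correlation r, then c = 1/√(2(1−r)). The rate would be 15.9% at r = 0.5, 9.8% at 0.7 and 1.3% at 0.9.

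The plan's repeated reference to test-retest SDs makes the SD of the retest difference the natural choice.

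**Step 4: practice gain.** If a gain of g SDs were not removed, the rate would be 1 − Φ(c − g). For an assumed g of 0.3 or 0.5, that is 24.2% or 30.9% at c = 1, and 8.9% or 12.6% at c = 1.645. The Synopsis compares change with expected test-retest change, which can be read to include the mean retest gain.

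**Step 5: the price of fixing a multiplier.** At a true shift of 1 SD of change, the pass rate is 1 − Φ(c − 1): 50.0% at c = 1, 25.9% at 1.645 and 16.9% at 1.96. A stricter cut-off lowers the chance rate and also loses half or more of the true responders in a ten-subject pilot. Neither end is wrong.

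**Step 6: what depends on the count.** The condition for a follow-up trial refers to a trend in the cognitive data. The follow-up sample size is to use whichever cognitive measure responds most. Neither names a responder proportion, and no section promises to report one. The mean and SD of change are computed without the rule.

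**The case for a change.** The strongest case for amending runs as follows. Individual classification is planned, since the Synopsis says results will be judged for individuals as well as the group. The cross-references name an SD but give no cut-off and are not tied to the Section 6 sentence. Even on the readings that survive, two responders of 10 has a chance probability of either 48.7% or 2.5%. The published SDs come from other populations and may be too small for cognitively impaired patients: at 1.645, a change SD 1.25 or 1.5 times larger (assumed) would raise 5% to 9.4% or 13.6%. If success on any one of the seven cognitive tests made a subject a responder, the chance rate per subject would be 30% at 5% per task, or 70% at 15.9%, assuming independent tests. The remedy is a line of text.

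Part of this stands. The multiplier is missing, and a cut-off chosen after unblinded inspection is weaker evidence than one fixed beforehand. But the rule is worded per task, and nothing in the plan turns it into an any-test rule. Doubt about whether published SDs suit this population would remain under any multiplier, and stating one would not cure it. With ten subjects, every individual change can be shown, so a reader can apply any cut-off. The concern about a second age allowance is speculative: on age-normed scores the expected change from ageing is zero.

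**Conclusion.** The wording is loose, but the gap is one that an analyst fills from the plan itself: a positive margin based on the published test-retest SD, with the multiple stated when results are reported. What remains open is a chance rate per task between 2.5% and 15.9%, or 0.25 to 1.6 of 10 subjects. This assumes normal change, no drug or practice effect, and an SD that is that of the retest difference. The literal 50% and 84% readings do not survive the rest of the document.

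Following the plan as written leads to no wrong result, because no go-ahead decision, sample size or promised report uses the responder count, and the group summary of change does not involve it. Prescribing a multiplier would exchange chance responders for missed ones (25.9% rather than 50.0% passing at a true 1-SD shift). That is a matter of preference in a single-arm pilot meant to assess safety and select outcomes. No change is called for.

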study drug and at the end of the study while still on the study drug. An asymmetry in power (roughly an integration of amplitude and frequency) in the affected side of the brain compared to the unaffected (or less affected) side of the brain, will be quantified as previously described (Hatfield et al., 2007; Ewen et al., 2009) for the quantitative EEG analysis. EEGs will occur at both sites, KKI and CCHMC, and the de-identified EEGs will be sent to KKI for analysis. The reason for this analysis is as a non-invasive biomarker of brain function which could be useful to develop as a marker of drug response. Quantitative EEG power analysis reflects an integration of the EEG activity amplitude and frequency. Therefore asymmetry of power on gEEG for these subjects reflects the increased slowing and decreased amplitude frequently seen in these patients interictally as their neurologic involvement progresses. Even patients with bilateral brain involvement have more involvement on one side than on the other side. Power asymmetry on gEEG has been shown to correlate with brain perfusion, brain atrophy, and SWS neuroscore, therefore, it has the potential as a biomarker responsive to monitor sirolimus treatment, both from the standpoint of safety and efficacy in a future larger clinical trial.

 Neuropsychological testing will be done at baseline and after six months on study drug.

Change over six months in cognitive functioning in Sturge-Weber syndrome is the primary outcome measure. This outcome will be assessed using a panel of testing selected based upon extensive experience in testing cognitive function in adults and children with SWS at the Kennedy Krieger Sturge-Weber Center. These will include the following measures from the National Institute of Health Toolbox (Gershon et al., 2010):

Attention/Executive Function – Flanker Inhibitory Control and Attention Test (Eriksen & Eriksen, 1974)

Executive Functioning – Dimensional Change Card Sort Test (Zelazo, Frye, & Rapus, 1996)

Episodic Memory – Picture Sequence Memory Test (Bauer et al., 2013; Dikmen et al., 2014)

Language – Oral Reading Recognition Test

Language - Picture Vocabulary Test (Dunn & Dunn, 1981)

Processing Speed – Pattern Comparison Processing Speed Test (Carlozzi et al., 2014)

Working Memory – List Sorting Working Memory Test (Weintraub et al., 2013)

Dexterity – 9-hole Pegboard Dexterity Test (Wang, Bohannon, Kapellusch, Garg, & Gershon, 2015)

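### Cognitive change is corrected for age and for retest scatter but not for the mean gain from repeating the tests, so any such gain counts as response to sirolimus

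*Combined protocol and SAP*

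**What the plan says.** The cognitive panel is given twice. Section 5.3 (Laboratory tests and clinical procedures) says: "Neuropsychological testing will be done at baseline and after six months on study drug". The Synopsis (Statistical Considerations) states: "There is no control group in this study of subjects who are not receiving study drug".

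Two yardsticks are named for judging the change:

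- **Age norms.** Section 6 says the tests "are normed to aged matched normal controls" and defines responders as "subjects whose normed results improve on the task more than what is expected for the increase in age (6 months", give or take an expected standard deviation.
- **Retest SDs.** The Synopsis says: "The published test-retest standard deviations will be used to determine whether changes in testing results exceed expected test-retest changes in results". Section 5.3 repeats the idea: "There are also published test-retest standard deviations from which to ascertain how much of a change in score is needed" before a change counts as significant.

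For the group, the Synopsis takes the final minus the initial score: "Mean and standard deviation of this difference for all 10 subjects will be calculated". It states no null value and no significance test for this difference.

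Section 6 gives the result two uses. The cognitive outcome that appears to respond most supplies the sample size of the follow-up trial. A suggestion of cognitive benefit, together with the absence of serious adverse events thought possibly or probably due to the drug, leads to planning that trial.

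Neither the Synopsis, Section 5.3 nor Section 6 mentions practice or learning effects, a mean retest gain, or alternate test forms.

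**The concern.** A before/after change in a performance test can contain growth with age, random retest scatter, the mean gain from having met the task before, other drift, and a drug effect. The plan handles the first two. Norms describe how a person of a given age scores, and a retest SD describes how widely changes spread. Neither says where changes are centred when nothing but repetition has happened. With no untreated group, nothing else in the design estimates that centre.

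Any mean practice gain therefore passes into the responder count and the mean change. It also affects the ranking of outcomes, because a test with a larger practice gain looks more responsive to the drug. That bears directly on the stated objective of finding the best outcomes for a later trial. The placebo-controlled trial would not repair an inflated planning effect: practice occurs in both of its arms and cancels in the comparison, so the effect used to size it would be too large.

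**Working it through.** The plan gives no practice gain, no SD value, no responder rate and no test for the cognitive change, so there is no figure of its own to reproduce. What can be computed is what the stated yardsticks return when the drug does nothing.

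**Inputs from the documents:** n = 10 (Synopsis and Section 6); two administrations (Section 5.3); no control group (Synopsis); yardsticks of age norms and test-retest SD (Synopsis, Sections 5.3 and 6).

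**Assumptions, because the documents are silent:** changes are normal, in units of the SD of retest change; practice gain g = 0, 0.2, 0.3 or 0.5; responder cut-off k = 1, since Section 6 fixes no multiple; no drug effect and no other drift.

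**1. Chance that one subject is a responder on one test,** P = 1 − Φ(k − g), at k = 1:

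- g = 0: 1 − Φ(1.0) = 0.159, or 1.6 expected responders of 10
- g = 0.2: 1 − Φ(0.8) = 0.212, or 2.1 of 10
- g = 0.3: 1 − Φ(0.7) = 0.242, or 2.4 of 10
- g = 0.5: 1 − Φ(0.5) = 0.309, or 3.1 of 10

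With a stricter cut-off, k = 1.96, the four values are 0.025, 0.039, 0.048 and 0.072. A positive g raises the rate at any cut-off.

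**2. Chance that the mean of 10 is positive,** P = Φ(g√10), with √10 = 3.162:

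- g = 0: Φ(0) = 0.50
- g = 0.2: Φ(0.632) = 0.74
- g = 0.3: Φ(0.949) = 0.83
- g = 0.5: Φ(1.581) = 0.94

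**3. Ranking of two inert tests,** one with gain g and one with none. The chance that the first shows the larger mean change is Φ(g√10 / √(2 − 2ρ)), where ρ is the correlation between their changes. At ρ = 0.5 the divisor is 1, so the values are those of step 2: 0.74, 0.83 and 0.94. At ρ = 0 they are Φ(0.447) = 0.67, Φ(0.671) = 0.75 and Φ(1.118) = 0.87. With equal gains the chance is 0.50.

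**4. Effect carried forward.** Suppose a true effect of 0.3 SD and a practice gain of 0.3 SD (both assumed). The pilot reads 0.6 SD. Sample size scales with 1/effect², so the next trial would be planned at (0.3/0.6)² = 0.25 of the size it needs.

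**5. Drift the other way.** If the net no-drug shift were −0.2 SD, the responder chance would be 1 − Φ(1.2) = 0.115 and the chance of a positive mean Φ(−0.632) = 0.26. The yardsticks would then understate benefit.

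**6. After the correction.** If the published mean gain applies to these patients and is subtracted first, the responder chance returns to 0.159 at k = 1 (0.025 at k = 1.96) and the chance of a positive mean to 0.50, whatever g is.

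**The case against.** The best textual defence is that the Synopsis compares changes with those expected on retest, and an expected change could include a mean shift. That wording does not settle the matter, because the only quantity supplied for it, there and in Sections 5.3 and 6, is a standard deviation. If a mean shift was intended, it has to be written in.

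A reader might infer that the plan is biased towards benefit overall. The documents do not support that. They report no practice gain for any test, at six months or in cognitively impaired patients. The Synopsis describes EEG slowing as neurologic involvement progresses, and the Background describes strokes and brain atrophy. Scores normed to healthy peers could therefore fall without drug. The practice component can only push upward; the net drift is unknown.

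A reader might also want to attach an inflated false-positive rate. The plan states no significance test, alpha or sidedness for the cognitive change, so no such rate describes it. The +1 SD cut-off used above is likewise an assumption.

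Nor does a trend alone launch the next trial. Section 6 also requires the safety condition and says the follow-up happens only if warranted. The plan discloses the missing control group and leaves confirmation to a randomized placebo-controlled trial. What remains at risk is the choice of outcome, the planning effect size and half of the go rule.

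Finally, the documents say only that published retest SDs exist. Whether mean gains are published for ages 3 to 31 at about six months cannot be checked here. The PROMIS self-report and grip strength are not shown to be subject to practice and are outside this point.

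**Conclusion.** The point holds as a gap in the stated method. For the performance-based cognitive and dexterity tests, the plan names a correction for ageing and one for scatter, but none for the mean gain on repetition, and no control group supplies it. Any such gain is credited to sirolimus.

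Its size cannot be established from the documents. The rises computed in steps 1 and 2 of the working are illustrations that rest wholly on the assumed gain, the assumed cut-off, and the absence of a drug effect or other drift. With zero gain there is no practice bias, and with enough decline from disease the net error reverses. The change is worth making because a silent assumption of zero gain feeds decisions that the pilot exists to inform.

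**What to change.** In the Synopsis (Statistical Considerations) and Section 6, for the performance-based cognitive and dexterity tests, define responders, the group trend and the ranking of outcomes on

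(six-month minus baseline age-adjusted score − published mean retest gain) / SD of retest change.

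- State the cut-off in these units, and the source and retest interval of each constant.
- Report the unadjusted change beside the adjusted one.
- Use an alternate form at six months where the battery has one.
- Where no published mean gain exists for the age range or interval, say so, and do not describe the uncontrolled change as a response to sirolimus.
- State as a limitation that drift from disease progression is not estimated.

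The cost is a wording change and one extra constant per test where one can be found; no added patients or visits are needed. The downside is possible over-correction, since published gains may come from shorter intervals or unimpaired people. Showing both versions lets the reader see how much depends on it.
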